9.4.3 ANALYSIS OF THE SECONDARY ENDPOINT(S)

For secondary endpoints, , we will follow Hochberg's step-up approach as outlined in Figure 2.

Figure 2. Decision structure for hypothesis testing of primary and secondary endpoints

Coupled with our primary hypothesis that CBT-I will result in improved ISI scores, a secondary hypothesis is that CBT-I will result in *greater improvement in* quality of life, as captured by the more general SF-12 that will be measured pre- and post-intervention in both the CBT-I and mEUC participants. We will use the validated method of Brazier et al. to calculate utilities (QALY penalties) from baseline and post-intervention SF-12 data by first mapping responses to the simpler SF-6D scale and then using a regression model to estimate single index scores.^{97, 98}_The cost-effectiveness analysis will compare incremental costs and quality-adjusted life years (QALYs) gained in the CBT-I arm compared with mEUC. The primary cost-effectiveness analysis will be from the payer's point of view (government, insurer, or health

18 May 2022

organization). The secondary cost-effectiveness analysis will be from the patient's point of view and include out-of-pocket medical costs and costs of lost productivity (both due to participation in Somryst sessions and due to poor sleep quality). For the main analysis from the payer's point of view, we will include cumulative CBT-I costs for the intervention arm payers and patients' combined costs to access and complete the web-based CBT-I intervention), and for both CBT-I and mEUC we will gather cumulative utilization data on medications, office visits, emergency department visits, and hospitalizations over the follow up period. We anticipate that most of these data can be gathered from EPIC the electronic health record (EHR) used in the AIM Clinic and New York Presbyterian Hospital, but participant follow up interviews will both validate electronic record data and capture any health care utilization at outside clinics and hospitals. Health facility visit costs will be entered as the reimbursement for that visit type specified by the Centers for Medicare and Medicaid Services⁹⁹ fee schedule. Mean wholesale medication prices will be estimated from the most recent "Redbook" listing of wholesale drug costs. For the secondary analysis from the patient's point of view, we will analyze data from participant interviews data on out-ofpocket medication costs, office visit co-pays, and lost compensation and missed work. Productivity losses will be estimated by multiplying age-specific labor force participation rates by average age-specific U.S. adult annual earnings for the participant's time observed in in the trial. Sources for average annual earnings (Current Population Survey 2014), labor force participation rate (Bureau of Labor Statistics, BLS), and consumption costs (BLS Consumer Expenditure Survey) were summarized in the Second Panel of Cost-Effectiveness.

Cost-effectiveness will be assessed based on the study observation period (9 weeks) in the main analysis, but micro- simulation analyses will simulate sustaining the insomnia prevention effects of CBT-I and EUC for years into the future, up to 10 years. Incremental cost-effectiveness ratios (ICERs) will be calculated as incremental change in costs divided by incremental change in QALYs comparing Somryst to mEUC).). ICERs will be assessed as follows (in 2021 U.S.): <50,000 per QALY gained will be considered cost-effective, \geq 50,000 and <150,000 of intermediate value, and \geq 150,000 of low value. Non-parametric bootstrapping with 1,000 random samples of all QALY and cost distributions

will be used to generate 95% uncertainty intervals for cost- effectiveness ratios.¹⁰⁰ Sensitivity analyses will test the robustness of the cost-effectiveness estimate to a range of inputs regarding intervention costs, productivity and quality of life losses related to chronic insomnia, size of quality of life improvement effect, and durability of intervention effect (ranging from one month to ten years). Cost-effectiveness analyses will be carried out and reported according to the Consolidated Health

Economic Evaluation Reporting Standards (CHEERS).¹⁰¹ Cost-effectiveness analyses will be carried out in TreeAgesoftware (TreeAge Inc., Williamstown, MA)

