Other Measures: *Sociodemographic Information* will be collected at screening including, age, sex, race, country of origin, educational attainment, nativity status, household income, employment status, and health insurance status. **Direct health care costs** will consist of the retail costs of Somryst (payer's costs plus patient out-of-pocket costs). Structured interviews will gather information about health care utilization (primary care, other ambulatory care, emergency department, or hospital visits). **Indirect costs** will include patients' lost productivity due to 1) participating in Somryst sessions, and 2) lost productivity related to poor sleep quality.

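### The main cost-effectiveness analysis is labelled payer perspective, but its Somryst cost includes what patients pay, so the label and the content of the main ICER conflict

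*Combined protocol and SAP*

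**What the plan says.** Section 9.4.3 names the perspective of the main economic result: "The primary cost-effectiveness analysis will be from the payer's point of view (government, insurer, or health" organization). For that same analysis it then specifies the cost of the intervention arm as payers' and patients' "combined costs to access and complete the web-based CBT-I intervention". An opening bracket seems to have been lost before the word for payers; the meaning is not affected.

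Section 8.1, under Other Measures, defines direct health care costs as the "retail costs of Somryst (payer's costs plus patient out-of-pocket costs"). It puts productivity lost through Somryst sessions under indirect costs.

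The second analysis in Section 9.4.3 takes the other side: "The secondary cost-effectiveness analysis will be from the patient's point of view and include out-of-pocket medical costs and costs of lost productivity". Its interview items are out-of-pocket spending on medication, co-pays for office visits, lost pay and missed work. A fee for Somryst is not named among them.

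For both arms, Section 9.4.3 enters visits at the Medicare/Medicaid fee-schedule reimbursement and drugs at mean wholesale price. It mentions no deduction of the patient's share. The ICER is incremental cost over incremental QALYs, the main horizon is 9 weeks, and the result is classified by fixed cut-offs, starting with "<50,000 per QALY gained will be considered cost-effective" and ending with low value at 150,000 or more.

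**The concern.** A payer-perspective analysis tells a government, insurer or health organization what it spends per QALY gained. Money that patients pay is not part of that. Here the label says payer, while the cost definition adds the patient's part of the Somryst cost. An analyst who follows the cost definition does not produce a payer ICER, and one who follows the label must depart from the cost definition. Two competent analysts could therefore report different main results from the same text.

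This matters for the economic result because Section 1.3 gives cost-effectiveness as a stated purpose of the trial, and because a single ratio is sorted into three value classes. Over 9 weeks the QALY denominator is small, so even a modest cost item can move the ratio a long way.

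**Working it through.** **Step 1. Compare label and content.**

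| Item | Main analysis | Second analysis |
|---|---|---|
| Stated perspective (9.4.3) | Payer | Patient |
| Somryst cost (9.4.3) | Payers' and patients' costs combined | Not named in the item list |
| Patient time on Somryst (9.4.3) | Not stated; the words on completing the program could be read to include it | Counted as lost productivity |
| Visits and drugs (9.4.3) | Fee schedule and wholesale price, no deduction of co-pays mentioned | Co-pays and out-of-pocket drug costs |

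The conflict lies within Section 9.4.3. Section 8.1 supports the reading that the combined cost is intended, although it names no perspective. The boundary for time matters because Section 6.1.2 expects up to 12 hours of participation per Somryst user.

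**Step 2. Effect on the ratio.** The plan gives no ICER, Somryst price, patient share or expected QALY gain, so there is no figure to reproduce. From the plan's own formula, with

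- p = mean Somryst cost borne by patients (Somryst arm only),
- c = between-arm difference, Somryst minus mEUC, in the patient-borne part of visit and drug costs as priced,
- dQALY = incremental QALYs, taken as positive,

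reported ICER − payer-only ICER = (p + c) / dQALY.

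The Somryst component alone adds p / dQALY, which is zero if p = 0 and positive if p > 0. The term c can have either sign. If mEUC patients use more visits or drugs, c is negative and offsets p in part or in full.

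**Step 3. Illustration of p / dQALY.** The utility gain u is an assumption (0.02 to 0.10), not a figure from the documents. Over the stated horizon, dQALY = (9/52) × u × f, with f = 0.5 if the gain builds up linearly and f = 1 if it is present throughout.

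| u | f | dQALY | Shift per $100 of p ($/QALY) | p that shifts the ICER by 50,000 |
|---|---|---|---|---|
| 0.02 | 0.5 | 0.00173 | 57,778 | $87 |
| 0.02 | 1 | 0.00346 | 28,889 | $173 |
| 0.05 | 0.5 | 0.00433 | 23,111 | $216 |
| 0.05 | 1 | 0.00865 | 11,556 | $433 |
| 0.10 | 0.5 | 0.00865 | 11,556 | $433 |
| 0.10 | 1 | 0.01731 | 5,778 | $865 |

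Example, first row: (9/52) × 0.02 × 0.5 = 0.00173; 100 / 0.00173 is about 57,800 (57,778 before rounding); 50,000 × 0.00173 is about 87.

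The table shows sensitivity, not an estimate of the error. Neither p nor dQALY is known.

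**The case against.** The strongest reply is that the consequence is unproven. No section says that participants pay anything for Somryst; Section 8.1 only names a patient component of the retail cost, without a split. If p is zero, nothing changes. This stands as a limit on size and is why the effect is stated conditionally. It does not remove the conflict, because the plan itself names a patient part and adds it in.

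A second reply is that the main analysis seems to price every resource without asking who pays. Visits and drugs carry no deduction of co-pays in either arm, so patient-borne costs may enter both arms. This also stands. A reader might infer that the payer ICER is biased upward; the documents do not support that without the conditions in Step 2, because c can offset p.

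A third reply is that sensitivity analyses over intervention cost are planned. They could show the effect of a lower, payer-only cost. But they vary an input and do not define the perspective of the main result.

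A reader might also infer that patients' Somryst costs are counted twice, since the patient analysis covers out-of-pocket medical costs. The documents do not support this. The two analyses are separate perspectives and no sum of them is planned, so a cost that appears in each is not double counting. It is not even clear that a Somryst fee enters the patient analysis, as its item list omits one.

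**Conclusion.** The point holds as an internal inconsistency: the main cost-effectiveness analysis carries a payer label and a payer-plus-patient cost for Somryst. Followed as written, it yields a ratio that is not a payer ICER. Nothing elsewhere in the plan corrects this.

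The effect of the patient-borne Somryst cost is p / dQALY, upward if both are positive. Under the assumed utility gains this is about $5,800 to $57,800 per QALY for each $100 of p. The actual size is unknown, and the net direction depends also on how co-pays on visits and drugs differ between arms. The issue is confined to the economic analysis and does not touch the ISI endpoint, the power calculation or the planned hypothesis tests. It should be settled before the economic analysis is run, because the choice of cost content could decide the value class.

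**What to change.** Choose one of two routes in Section 9.4.3 and align Section 8.1 with it.

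1. **Keep the payer perspective.** Count only what the payer pays for Somryst and, for consistency, enter visits and medications net of patient co-pays and out-of-pocket spending in both arms.
2. **Keep the combined cost.** Relabel the main analysis as payer plus patient direct health-care costs (a health-care-sector perspective). This fits the way visits and drugs are already priced.

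Under either route, state in which analysis patients' Somryst fees are counted and in which their time is counted.

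The second route costs wording only, but then the main result no longer answers the payer's question. The first needs more. Co-pays for office visits and out-of-pocket medication costs are already planned interview items, but the documents do not show that the payer and patient parts of the Somryst cost are recorded separately. That split may have to be a stated assumption, varied in the sensitivity analysis already planned for intervention costs.

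### The productivity-loss formula in the patient-perspective cost-effectiveness analysis gives expected total earnings, not a loss, and cannot register a treatment effect

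*Combined protocol and SAP*

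**What the plan says.** Section 8.1 (Other Measures) defines indirect costs as "patients' lost productivity due to 1) participating in Somryst sessions, and 2) lost productivity related to poor sleep quality". Section 9.4.3 carries the same two components into the secondary, patient-perspective cost-effectiveness analysis, which is to include out-of-pocket medical costs and "costs of lost productivity (both due to participation in Somryst sessions and due to poor sleep quality".

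Later in Section 9.4.3, the data for this perspective are said to come from participant interviews on "out-ofpocket medication costs, office visit co-pays, and lost compensation and missed work". The next sentence gives the only formula for the productivity term: "Productivity losses will be estimated by multiplying age-specific labor force participation rates by average age-specific U.S. adult annual earnings for the participant's time observed" in the trial. Earnings are taken from the 2014 Current Population Survey, and the cost-effectiveness thresholds are expressed in 2021 dollars. The same section sets the horizon of the main cost-effectiveness analysis at 9 weeks.

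**The concern.** The quantity to be measured is productivity lost. The quantity the formula returns is participation rate times annual earnings times time observed, which is expected total earnings. Two participants of the same age and length of follow-up receive the same value whether one missed no work and the other missed several weeks. The value depends only on age, which randomization balances in expectation, and on time observed.

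At stake is the productivity term of the patient-perspective ratio. Both indirect costs that Section 8.1 sets out to capture depend on treatment: session time is incurred only in the Somryst arm, and work lost to poor sleep should fall if the program works. A term that responds to neither leaves the patient-perspective result without the contrast it was meant to contain. An analyst who followed the formula and one who followed the interview data would report different ratios from the same trial.

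**Working it through.** The documents state no productivity figure, so there is none to reproduce. The check evaluates the formula as written and compares it with one that contains lost time.

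**Inputs from the documents**
- Formula and 9-week horizon: Section 9.4.3.
- Session time of up to 12 hours in the Somryst arm: Section 6.1.2.
- 200 patients allocated 1:1, so 100 per arm; attrition of up to 15% overall, with no per-arm figure: Sections 6.3 and 9.2.

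**Assumptions, not in the documents**
- Participation rate p = 0.60 to 0.80; annual earnings E = $30,000 to $70,000; 2,080 working hours a year.
- Fraction of working time lost, f: 5% (Somryst) versus 10% (mEUC).
- Dropout of 20% versus 10%, which averages to the plan's 15%.

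**Step 1. The formula as written.** L = p × E × T/52, with T = 9 weeks.
- Low: 0.60 × 30,000 × 9/52 = $3,115
- Middle: 0.70 × 50,000 × 9/52 = $6,058
- High: 0.80 × 70,000 × 9/52 = $9,692

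This is the whole of expected earnings for the window. It amounts to setting f = 1 for everyone.

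**Step 2. With a lost-time factor.** Loss = f × L, so the arm difference is (0.05 − 0.10) × L.
- Low −$156, middle −$303, high −$485 per patient.
- Formula as written, same inputs and equal follow-up: L − L = $0.

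**Step 3. Session time left out.** 12 × p × E/2,080.
- Low: 12 × 0.60 × 30,000/2,080 = $104
- High: 12 × 0.80 × 70,000/2,080 = $323 per Somryst patient.

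**Step 4. Chance variation.** In 4,000 simulated trials of 100 per arm with equal follow-up, p = 0.70, E = $50,000, an assumed lognormal spread of earnings values (log-scale SD 0.3) and f averaging 5% versus 10%:
- as written: mean arm difference −$2, SD across trials $272;
- with the lost-time factor: mean −$318, SD $54.

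The −$318 is slightly larger than the −$303 in Step 2 because that spread raises mean earnings by a factor of exp(0.3²/2) = 1.046. The formula as written misses the effect and has about five times the sampling spread (272/54).

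**Step 5. Unequal time observed, dropout 20% versus 10%.**
- Dropouts observed for half the window: (1 − 0.5 × 0.20) − (1 − 0.5 × 0.10) = 0.90 − 0.95 = −0.05, so −0.05 × L = −$156 to −$485.
- Dropouts contribute no time: 0.80 − 0.90 = −0.10, so −0.10 × L = −$312 to −$969.
- Dropout of 15% in both arms: $0.

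**The case against.** The best defense is that lost time is partly collected already. Interviews on "lost compensation and missed work" are planned for this same perspective, and the product may have been meant only as the wage value to apply to that time. This stands as far as it goes: a reader might infer that missed work is not measured at all, and the text does not support that. Nor does the lack of a missed-work row in the Section 1.3 schedule show that the items are uncollected, because the schedule lists instruments and domains. But nothing in Section 9.4.3 links the formula to the interview data, and no other section supplies the missing factor.

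Section 9.4.3 also plans sensitivity analyses over productivity losses. Varying the inputs does not add a term that the formula lacks.

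Three stronger readings are tempting and are not supported.
- *That the plan favors the arm with more dropout.* This requires loss to follow-up that differs between arms. Section 9.2 gives only an overall figure, and under Section 7.1 participants who stop Somryst alone remain in all later assessments. The direction is certain; whether it occurs, and by how much, is unknown. Nor would every non-zero difference reflect follow-up, since chance age imbalance produces one too.
- *That the distortion should be computed over the full follow-up to 6 months and converted to dollars per QALY.* The stated horizon of the main analysis is 9 weeks, and patients who leave after that point are fully observed within it. Utilities come from baseline and 9-week SF-12 data, and the documents give no expected QALY gain to divide by.
- *That 2014 earnings are an error beside 2021 dollars.* The plan does not say that earnings will be left uninflated. The step is merely unstated.

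**Conclusion.** The formula is wrong as written. It values all expected earnings over the time observed, so its expected arm difference is about $0 for any treatment effect on work. With an assumed 5% versus 10% of time lost over 9 weeks, it would miss a difference of $156 to $485 per patient. It also leaves out session time worth about $104 to $323 per Somryst patient. If time observed is unequal, the arm observed for less time looks cheaper, by $156 to $969 per patient across the dropout scenarios examined.

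These amounts rest on assumed participation, earnings, lost time and dropout, and serve only to show scale. The main conclusion, that the formula does not respond to lost time, needs none of them. The reach is limited to one term of a secondary analysis: the ISI endpoint and the primary, payer-perspective cost-effectiveness analysis do not use it.

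**What to change.** Replace the formula sentence in Section 9.4.3 with: productivity loss = (interview-reported work time missed or impaired because of poor sleep + work time displaced by Somryst sessions) × a wage value. Use the participation- and age-specific earnings only as that wage value, expressed in 2021 dollars. Compute the loss over the fixed analysis horizon, not scaled by each participant's time observed.

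Three supporting changes are needed.
- Confirm that the planned interview captures both missed and impaired work, with a stated recall period, at each assessment. Add two or three questions if it does not, and show the items in the Section 1.3 schedule.
- State how incomplete cost follow-up is handled. The missing-data text in Section 9.4.2 concerns the outcome models, but the multiple imputation named there could be extended to costs.
- State whether the participation rate stays in the wage value once work time is reported directly, and how session time is valued for participants without paid work. Both are valuation choices for the study team.

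The cost is slightly more analysis work and possibly a few extra interview items, with no new visit.
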